3.3 Study Duration and Dates

The study will continue until at least 12 surgical procedures (including a minimum of 6 major surgeries, of which at least 5 must be procedures other than central venous access device placement) have been performed in at least 6 patients.

The duration of the patient's participation in the study (from signing the Informed Consent form until the last follow-up visit) may vary. In patients undergoing a major procedure the duration of participation will be approximately 6 to 9 weeks (or longer if treatment with LR769 is extended). In patients undergoing a minor procedure the duration of participation will be approximately 5 to 8 weeks (or longer if treatment with LR769 is extended).

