9.5 Efficacy Endpoints

Efficacy results will be reported as descriptive statistics. Surgeries will be examined overall as well as by major procedures and minor procedures separately.

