9.5.2 Secondary Efficacy Endpoints

The secondary efficacy endpoints are:

- Percentages of success as defined as the combination of “good” and “excellent” responses by the investigator or designee for all efficacy timepoints other than the primary
- Percentages of “poor,” “moderate,” “good,” and “excellent” response by the investigator or designee for all efficacy timepoints
- Percentages of success as defined as the combination of “good” and “excellent” responses by the surgeon/practitioner
- Percentages of “poor,” “moderate,” “good,” and “excellent” response by the surgeon/practitioner for the intraoperative period
- Intraoperative blood loss determined by the surgeon/practitioner as compared to the surgeon/practitioner’s maximum predicted blood loss
- Number of events requiring transfusion between start of procedure and 48 (\pm 4) hours after last administration of LR769
- Changes in hemoglobin between start of procedure and 48 (\pm 4) hours after last administration of LR769
- Amount of LR769 used. Total, and separated by use in hospital, at home, or for specific reasons (eg, physical therapy, or other reasons like drain or suture removal)
- Number and type of bleeding episodes at the surgical site between start of procedure and 48 (\pm 4) hours after last administration of LR769
- Number of surgical interventions/re-explorations for bleeding episodes between start of procedure and 48 (\pm 4) hours after last administration of LR769

Point estimates will be computed together with 95% confidence intervals for the proportion of successes, mean difference between intraoperative blood loss and surgeon/practitioner’s maximum predicted blood loss, proportion of events requiring transfusion, mean hemoglobin level at each timepoint, mean amount of LR769 used, and mean number of surgical interventions/re-explorations for bleeding episodes. Clopper-Pearson exact confidence intervals will be used for dichotomous endpoints; confidence intervals for continuous variables will be based on the normal approximation.

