4. SAMPLE SIZE AND POWER CALCULATION

The sample size was determined based on adaptations of international guidelines for coagulation factors and after United States (US) and European Union (EU) health authority consultations. The study will continue until at least 12 surgical procedures (including a minimum of 6 major surgeries, of which at least 5 must be procedures other than central venous access device placement) have been performed in at least 6 patients.

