7.7 Efficacy Endpoints and Analysis

All the Efficacy analyses will be stratified by surgery type and overall. All analyses will then be repeated stratifying by age group (< 12 years and \geq 12 years). Efficacy population will be used for all the analyses described in this section.

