7.7.2 Analysis of Secondary Efficacy Endpoints

The following endpoints are considered secondary for this study:

- Percentages of success as defined as the combination of “good” and “excellent” responses by the investigator or designee for all efficacy timepoints other than the primary
- Percentages of “poor,” “moderate,” “good,” and “excellent” response by the investigator or designee for all efficacy timepoints
- Percentages of success as defined as the combination of “good” and “excellent” responses by the surgeon/practitioner for the intraoperative period
- Percentages of “poor,” “moderate,” “good,” and “excellent” response by the surgeon/practitioner for the intraoperative period
- Intraoperative blood loss determined by the surgeon/practitioner as compared to the surgeon/practitioner’s maximum predicted blood loss
- Number of events requiring transfusion between start of procedure and 48 (±4) hours after last administration of LR769
- Changes in hemoglobin between start of procedure and 48 (±4) hours after last administration of LR769
- Amount of LR769 used. Total, and separated by use in hospital, at home, or for specific reasons (eg, physical therapy, or other reasons like drain or suture removal)
- Number and type of bleeding episodes at the surgical site between start of procedure and 48 (±4) hours after last administration of LR769
- Number of surgical interventions/re-explorations for bleeding episodes between start of procedure and 48 (±4) hours after last administration of LR769

The first four secondary endpoints will be analyzed similarly to the primary endpoint: numbers and percentages of successes will be summarized at each timepoint, together with their Clopper-Pearson exact confidence limits.

Difference between the expected and actual blood loss will be calculated for each surgery in the study and then summarized together with 95% confidence limits. Number of events requiring transfusion, Number of bleeding episodes (by type) at the surgical site between start of procedure and 48 (±4) hours, and Number of surgical interventions/re-explorations for bleeding episodes between start of procedure and 48 (±4) hours after last administration of LR769 will be analyzed similarly.

Hemoglobin levels will be summarized at baseline and at 48 (±4) hours after last administration of LR769. Changes from baseline will also be summarized for 48 (±4) hours timepoint. 95% confidence limits for the changes will be displayed.

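### Normal-approximation 95% intervals for continuous secondary endpoints cover about 89% at the minimum of 6 major procedures, and the SAP names no other method

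*Protocol*

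**What the plan says.** On secondary endpoints, Protocol 9.5.2 states: "Point estimates will be computed together with 95% confidence intervals". The continuous quantities it lists are the mean blood-loss difference (actual against the surgeon's maximum prediction), mean hemoglobin at each timepoint and mean amount of LR769. Dichotomous endpoints get Clopper-Pearson intervals, whereas "confidence intervals for continuous variables will be based on the normal approximation". The synopsis says the same.

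SAP 7.7.2 covers this ground with less detail. "Difference between the expected and actual blood loss will be calculated for each surgery in the study", and the result is to be summarized with 95% limits; the hemoglobin change also gets 95% limits. No method is given for either. For the amount of LR769 the SAP asks for summaries only. SAP section 9, which records departures from the protocol, mentions only the dropped paired t-tests.

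On numbers, SAP section 4 lets the study end after "at least 12 surgical procedures (including a minimum of 6 major surgeries", and Protocol 3.3 adds that these "have been performed in at least 6 patients". On subgroups, Protocol 9.5 says: "Surgeries will be examined overall as well as by major procedures and minor procedures separately". SAP 7.7 agrees ("All the Efficacy analyses will be stratified by surgery type and overall") and goes further: "All analyses will then be repeated stratifying by age group", with a cut at 12 years.

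**The concern.** A normal quantile treats the standard deviation as known. Here it is estimated from as few as 6 values in the major-surgery group, where the hemostatic challenge is greatest. The interval is then too short for its label. No hypothesis test is planned for these endpoints, so the interval is the main statement of uncertainty a reader will have. If it is labelled 95% but covers less, the report overstates how precisely blood loss and hemoglobin change were measured.

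The plan is also uneven. It takes care to use an exact method for proportions in these small groups and, in the same sentence, a large-sample method for means.

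**Working it through.** **Figure to reproduce.** The documents give no power or precision calculation. The only stated figure is the nominal 95%, so the check is whether the stated rule delivers it.

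**Inputs.**
- Confidence level 95%, two-sided, so z = 1.960 (Protocol 9.5.2).
- Rule: normal approximation, read as mean ± 1.960 × SD/√n (Protocol 9.5.2 and synopsis).
- n = 12 overall and n = 6 major, both planned minimums (Protocol 3.3, SAP 4). Minor procedures have no minimum. Age cells have none either, and the group under 12 opens only after the DMC reviews PERSEPT 2 data.
- Assumption: procedures are independent and values normally distributed. The documents give no SD or distribution.

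**Coverage of the stated rule.** With an estimated SD, (sample mean − true mean)/(SD/√n) follows Student t on n−1 degrees of freedom. Actual coverage is therefore P(|t on n−1 df| < 1.960) = 2F(1.960) − 1, where F is the t distribution function. The multiplier needed for 95% is the 0.975 quantile of t.

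| n | Coverage of z interval | t quantile | t/z |
|---|---|---|---|
| 4 | 85.5% | 3.182 | 1.624 |
| 5 | 87.8% | 2.776 | 1.417 |
| 6 | 89.3% | 2.571 | 1.312 |
| 12 | 92.4% | 2.201 | 1.123 |

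At n = 6 the interval misses the true mean 100 − 89.3 = 10.7% of the time, more than twice the nominal 5%. Its half-width is 1.960/√6 = 0.80 SD where 2.571/√6 = 1.05 SD is needed. At n = 12 the half-widths are 1.960/√12 = 0.57 SD and 2.201/√12 = 0.64 SD.

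**Departures from the assumptions (simulation, illustrative only).**

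| Assumed data | n | z coverage | t coverage |
|---|---|---|---|
| Lognormal, CV 50% | 6 | 86% | 92% |
| Lognormal, CV 100% | 6 | 80% | 86% |
| Normal, 2 procedures per patient, intraclass correlation 0.2 | 6 | 85.8% | 92.9% |
| Same, intraclass correlation 0.5 | 6 | 80.0% | 88.6% |
| Same, intraclass correlation 0.2 | 12 | 89.5% | 92.7% |
| Same, intraclass correlation 0.5 | 12 | 84.7% | 88.7% |

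The clustered rows matter because SAP 7.1 lets a patient enter more than once and analyses efficacy by procedure. In the lognormal case with CV 100%, the shortfall is 95 − 80 = 15 points. The t quantile recovers 86 − 80 = 6 of them; the other 9 are due to skew, not to the multiplier.

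**The case against.** **The phrase need not mean 1.96.** No formula is given. The wording is set against an exact method and could mean limits computed under normality, which would allow a t quantile; the defect in width would then vanish. This is possible, but it is not the plain meaning. Protocol 9.6 names t-tests where it wants Student's t, and no section names a t interval. If t limits were intended, the SAP still has to say so.

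**Coverage of 80–89%.** A reader might infer that range as a property of the plan. The documents do not support the lower end. At n = 6 it needs an assumed distribution, such as a lognormal with CV 100%, or strong within-patient correlation. A lognormal also cannot represent the blood-loss difference, which can be zero or negative. For the overall analysis at n = 12, normal data give 92.4%.

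**Six per surgery type.** A reader might also take 6 as the floor for each type. It applies to major surgery only.

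**Error bars on drug use.** Only the protocol asks for an interval on the amount of LR769; the SAP does not.

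**Little depends on it.** This stands. Protocol 9.5 describes efficacy reporting as descriptive, no margin or decision rule is attached to these endpoints, and no conclusion turns on whether a blood-loss interval excludes zero. That limits the consequence, but it does not turn an 89% interval into a 95% one.

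**Conclusion.** The point holds for continuous secondary endpoints. Under the plain reading of Protocol 9.5.2, which the SAP does not replace, nominal 95% intervals cover 89.3% at 6 major procedures and 92.4% at 12 overall. Smaller minor or age cells fall lower: 87.8% at n = 5. These figures rest on three assumptions: the multiplier is 1.96, the procedures are independent and the values are normal. Right skew or repeat procedures would push coverage down further, but the size of that effect is unknown, and t limits would repair it only in part.

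This deserves correction because the error is definite and the remedy nearly free. It is not a threat to the trial's main result: the primary endpoint has a Clopper-Pearson interval and is untouched.

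**What to change.** In SAP 7.7.2, state that two-sided 95% limits for means of continuous endpoints are mean ± t(0.975, n−1) × SD/√n. In SAP section 9, list this as a change from Protocol 9.5.2 and the synopsis. Because the primary conclusions are not affected, SAP 7.1 does not call for a protocol amendment.

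For endpoints that prove skewed, rely on the median, minimum and maximum already planned in SAP 7.1. An exact interval for the median would add little. At n = 6 it is simply minimum to maximum, with confidence 1 − 2/64 = 96.9%. At n = 5 even the full range reaches only 1 − 2/32 = 93.75%.

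The cost is one sentence and one entry in the list of deviations. No data or patients are added. Intervals become 31% wider at n = 6 and 12% wider at n = 12.

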9.6 Safety Endpoints and Analysis

Safety endpoints include the following:

- Analysis (including relationship to LR769, severity, and outcome) of AEs/SAEs between first LR769 administration and 28 (\pm 3) days after last administration of LR769
- Analysis of treatment-emergent thromboembolic events between start of procedure and 28 (\pm 3) days after last administration of LR769

- Analysis of allergic and anaphylactic reactions between start of procedure and 28 (± 3) days after last administration of LR769
- Analysis of treatment-emergent antibodies against LR769 or host-related impurities between start of procedure and 28 (± 3) days after last administration of LR769

All AEs will be coded using the Medical Dictionary of Regulatory Activities (MedDRA). The number and percentage of patients with any treatment-emergent AEs (TEAEs) and any treatment-emergent serious AEs (SAEs) will be presented for all patients. An AE will be considered treatment related if it has a definite, probable, or possible relationship to the study treatment or if the relationship to the study treatment is missing. AEs will be summarized at the patient level by MedDRA system organ class (SOC) and preferred term (PT) using frequencies and percentages. AEs will also be tabulated at the event level by SOC, PT, and severity and by SOC, PT, and relationship to study treatment.

The number and percentage of patients with any treatment-emergent thromboembolic event and/or allergic and anaphylactic reactions will be presented for all patients.

For vital signs and clinical laboratory test results (continuous parameters), descriptive statistics for the actual value at each timepoint and the change from baseline to each post baseline timepoint will be tabulated. Two-sided paired t-tests will be used to test whether the mean changes from baseline equal 0. Baseline is defined as the last measurement prior to study treatment. Descriptive statistics for immunogenicity data will also be produced for the specified timepoints.

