4.3 Exclusion Criteria

Patients who meet any of the following criteria will be excluded from the study.

1. have any coagulation disorder other than hemophilia A or B
2. be immunosuppressed (ie, the patient should not be receiving systemic immunosuppressive medication; CD4 counts at screening should be $>200/\mu\text{l}$)
3. known intolerance to LR769 or any of its excipients
4. currently receiving ITI therapy
5. have a known allergy or hypersensitivity to rabbits
6. have platelet count $<100,000/\mu\text{L}$
7. have received an investigational drug within 30 days of the planned first LR769 administration, or is expected to receive such drug during participation in this study (with the exception of patients who are or were participating in another LR769 study, eg, a study assessing the treatment of bleeding episodes with LR769)
8. have a clinically relevant hepatic (aspartate aminotransferase [AST] and/or alanine aminotransferase [ALT] >3 times the ULN and/or renal impairment (creatinine >2 times the ULN)
9. have a history of arterial and/or venous thromboembolic events (such as myocardial infarction, ischemic strokes, transient ischemic attacks, DVT, or PE) within 2 years prior to the planned first dose of LR769, uncontrolled arrhythmia, or current New York Heart Association (NYHA) functional classification score of stages II – IV
10. have an active malignancy (those with non-melanoma skin cancer are allowed)
11. have any life-threatening disease or other disease or condition which, according to the investigator's judgment, could imply a potential hazard to the patient, or interfere with the trial participation or trial outcome (eg, a history of non-responsiveness to bypassing products)
12. be using aspirin, NSAIDS, herbs, natural medications, or other drugs with platelet inhibitory properties within one week prior to surgery and for the duration of treatment with LR769
13. have active gastric or duodenal ulcer disease

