6 STUDY PROCEDURES

6.1 Informed Consent

All patients will be informed of the aims of study, the possible AEs, the procedures and possible risks to which they will be exposed, and how treatment and dose will be determined. They will be informed as to the strict confidentiality of their personal data, and that their medical records may be reviewed for study purposes by authorized individuals other than their treating physician. It will be emphasized that participation is voluntary and that the patient is allowed to refuse further participation in the protocol whenever he wants. Once the patient completely understands the study and its procedures and risks, he will be asked to sign and date the Informed Consent. Study procedures may not begin until after the Informed Consent is signed and dated.

If the patient is younger than 18 years of age, his parent(s)/legal guardian(s) will receive the same information. His parent(s)/legal guardian(s) will sign and date the Informed Consent.

The patient may, depending on his age, receive age-appropriate information as well as be asked to sign and date an Assent form. Age of providing information and Assent form may differ among institutions and will be determined by local law and Institutional Review Board (IRB) or Independent Ethics Committee (IEC) requirements.

Once the Informed Consent and/or Assent has been signed and dated by the patient and/or parent(s)/legal guardian(s), the patient is considered enrolled in the study.

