6.9.2 Timing

Adverse events will be collected from the time of the signing of the Informed Consent/Assent until resolution or 30 days after the last dose or early termination, whichever comes first. At each specified timepoint, the patient (or parent/legal guardian) will be asked to report any and all AEs experienced since the previous assessment or visit. Specifically, the patient (or parent(s)/legal guardian(s) if the patient is a child), will be asked if the patient experienced any signs and symptoms that may indicate a thromboembolic event occurred. These may include, among others, headache, shortness of breath, chest pain, cyanosis, calf pain, swelling/edema, or redness.

If an AE occurs in PERSEPT 3 and the patient is still enrolled in PERSEPT 2, the AE should only be collected in PERSEPT 3. If the AE is ongoing at the time of rejoining PERSEPT 2, that AE should be only collected in PERSEPT 2 under medical history. If when rejoining PERSEPT

2, there is an exacerbation or recurrence of the AE, this AE should be collected as a new AE in [PERSEPT 2](#).

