7.1 Screening (Days -21 to -1)

- Informed consent signature
- Determine eligibility
- Demographics
- Medical history
- Physical examination
- Clinical safety laboratory tests (hematology, coagulation, serology, chemistry, urinalysis), by local laboratory - per weight requirement
- FVIII/FIX and inhibitor testing, by central laboratory (as confirmed at screening by the institutional lab, with the exception being for patients <12 kg where samples will only be collected for testing at the central laboratory)
- Vital signs
- 12-lead ECG
- Assessment of concomitant medication
- Assessment of AEs

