7.8.2 Adverse Events

All AEs will be coded using MedDRA (Version 15.0). An AE will be considered a treatment-emergent adverse event (TEAE) if it occurred or worsened after the first dose of study drug. In case a patient undergoes multiple procedures in the study, the TEAE will be assigned to the latest procedure prior to the event itself. Non-TEAEs are AEs occurring after signing Informed Consent but before the first administration of study drug. TEAEs will be summarized for the Safety Population. Non-TEAEs will be summarized for all enrolled patients.

The number and percentage of patients as well as the number of events will be summarized for any TEAEs, any treatment emergent SAEs, any treatment-related TEAEs, any non-treatment-related TEAEs, any TEAEs leading to discontinuation from the study, any TEAEs leading to study drug withdrawal and any TEAEs resulting in death. Summaries will be done stratifying by SOC and PT. An AE will be considered treatment related if it has a definite, probable, or possible relationship to the study treatment or if the relationship to the study treatment is missing. Additionally, a summary of TEAE's by SOC, PT, and severity grade will be created.

Separate summaries and listings will be provided for treatment-emergent thromboembolic events and allergic and anaphylactic reactions.

A data listing of TEAEs will be produced. Separate listings will also be prepared for SAEs, AEs leading to death, TEAEs leading to discontinuation from the study, TEAEs

leading to study drug withdrawal, thromboembolic AEs, and allergic and anaphylactic AEs. A listing of deaths will be provided as well, including information about the primary reason for death.

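### For a patient still in PERSEPT 2, a reaction to an LR769 dose given there during PERSEPT 3 screening can be treatment-emergent in neither trial

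*Protocol*

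**What the plan says.** **Concurrent participation.** Exclusion 7 (Protocol 4.3) bars investigational drugs within 30 days before the planned first dose and during participation, "with the exception of patients who are or were participating in another LR769 study".

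**Entry and collection.** Once consent or assent is signed, "the patient is considered enrolled in the study" (Protocol 6.1). Screening covers Days -21 to -1 (Protocol 7.1). "Adverse events will be collected from the time of the signing of the Informed Consent/Assent" (Protocol 6.9.2).

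**Routing.** Protocol 6.9.2 adds a rule for events that arise during PERSEPT 3: where "the patient is still enrolled in PERSEPT 2, the AE should only be collected in PERSEPT 3". Should the event still be ongoing when he rejoins the other trial, "that AE should be only collected in PERSEPT 2 under medical history". An exacerbation or recurrence on rejoining becomes a new AE there.

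**Classification.** "Non-TEAEs are AEs occurring after signing Informed Consent but before the first administration of study drug" (SAP 7.8.2). Protocol 6.9.1 and 6.9.9 say the same, and 6.9.9 makes an event present before the first dose treatment-emergent if it worsens afterwards.

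**Windows.** The AE/SAE endpoint in Protocol 9.6 covers "Analysis (including relationship to LR769, severity, and outcome) of AEs/SAEs between first LR769 administration and 28" (±3) days after the last dose. The thromboembolic, allergic and antibody endpoints open at the start of the procedure.

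**The concern.** The routing rule and the classification rule each make sense alone. Routing avoids counting one event in two trials. Classification separates background events from events on drug. The second rule assumes that the time between consent and the first dose is free of LR769. For a patient who is still being treated in PERSEPT 2, that need not be so.

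If a bleed is treated with LR769 under PERSEPT 2 during PERSEPT 3 screening, a reaction to that dose follows exposure to the drug. The rules would nevertheless file it here as a pre-treatment event and tell the other trial not to collect it as an AE. Safety, including immunogenicity, is the only secondary objective. In a trial whose stated minimum is 6 patients and 12 procedures, one event can visibly change a safety table.

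**Working it through.** No figure in the plan is at stake, so the check follows one event through the rules. The event begins after PERSEPT 3 consent, after an LR769 dose given under PERSEPT 2, and before the first PERSEPT 3 dose.

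| Step | Rule | Result |
|---|---|---|
| 1. May the patient be in both trials? | Protocol 4.3, exclusion 7; 3.1; 6.9.2 | Yes |
| 2. Is he in PERSEPT 3 yet? | Protocol 6.1, 7.1 | Yes, from consent, up to 21 days before the procedure |
| 3. Which trial collects the AE? | Protocol 6.9.2 | PERSEPT 3 only, if an AE during screening counts as occurring in PERSEPT 3 |
| 4. How is it classed? | Protocol 6.9.1, 6.9.9; SAP 7.8.2 | Non-TEAE, if the first dose means the first dose in this trial |
| 5. Is it inside the AE/SAE window? | Protocol 9.6 | No, on the same reading |
| 6. Is it inside the thromboembolic or allergic window? | Protocol 9.6 | No, on either reading, because onset precedes the procedure |
| 7. What does PERSEPT 2 record? | Protocol 6.9.2 | Nothing if resolved at rejoining; medical history if ongoing; a new AE if it recurs or exacerbates |

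The event is therefore counted as treatment-emergent here only if it worsens after the first PERSEPT 3 dose. It is recorded as an AE in PERSEPT 2 only if it recurs or exacerbates on rejoining. A reaction that resolves, or continues unchanged, is treatment-emergent in neither trial.

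**Two readings of the first administration.** The Protocol does not tie the phrase to this trial. Three features favour the in-study reading:
- The SAP writes of the study drug.
- Both documents define an interval from consent to first dose, which would be empty for anyone treated in PERSEPT 2 before consenting here.
- The Safety Population (Protocol 9.3) requires at least one dose of LR769. Counting doses from other trials would admit patients never treated in this one.

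**Illustration of size.** The documents give minimums only: 12 procedures in at least 6 patients (Protocol 3.3). Taking 6 to 12 patients is an assumption; 12 would mean one procedure each.
- One event in 12 patients: 1/12 = 8.3%. One event in 6: 1/6 = 16.7%.
- Exact 95% interval for 0/12: the upper limit is 1 − 0.025^(1/12) = 26.5%, giving 0 to 26.5%.
- Exact 95% interval for 1/12: the lower limit is 1 − 0.975^(1/12) = 0.2%. The upper limit solves (1 − p)^12 + 12p(1 − p)^11 = 0.025, so p = 38.5%.

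This shows what one event would do in a table of that size. It does not estimate how often such events occur.

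**The case against.** The case against is substantial, and most of it limits the size of the point.

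- **Thrombosis.** A reader might infer that a thrombosis during screening would disappear from the trial's thrombosis rate. Eligibility is confirmed again before the procedure (Protocol 7.2.1). A thromboembolic event within 2 years meets exclusion 9, and known intolerance to LR769 meets exclusion 3. Such a patient should not be dosed here, so on the in-study reading he is in neither numerator nor denominator. This stands.
- **Loss of the event.** A reader might infer that the event vanishes. It does not. Non-TEAEs are summarised for all enrolled patients. The SAP 7.8.2 listings of SAEs, thromboembolic AEs and allergic AEs are not restricted to treatment-emergent events. Relationship to LR769 is recorded for every AE (Protocol 6.9.4). SAEs, acute allergic reactions and confirmed thrombotic events keep expedited reporting (Protocol 6.9.8.2, 6.9.9). This stands.
- **A literal reading.** Protocol 6.9.9 can be read to include a dose given in PERSEPT 2, which would make the event a TEAE. That the window would then open before consent is harmless, since only AEs collected from consent onward would enter it. So it goes too far to say that no reading works for the AE/SAE endpoint. What remains is that the text allows two readings with different counts.
- **A pause in PERSEPT 2.** The routing sentence is conditional on the AE occurring in PERSEPT 3, and the word rejoining suggests that PERSEPT 2 may be suspended. If suspension began at consent, no PERSEPT 2 dose would fall in screening. The documents do not say when it begins, so this leaves the matter open.
- **Downward bias.** A reader might infer that the drug's incidence is biased downward. The procedure-based windows suggest that the main interest is the perioperative regimen, and pooling reactions to dosing in another trial would mix regimens. This argues for separate display. It does not justify leaving the event treatment-emergent nowhere.

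**Conclusion.** The point holds as a minor inconsistency. On the in-study reading, the written rules let a reaction to LR769 given under PERSEPT 2 during PERSEPT 3 screening be treatment-emergent in neither trial, subject to the exceptions for worsening, recurrence and exacerbation.

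This rests on three assumptions: that PERSEPT 2 dosing continues during screening, that an AE in screening counts as occurring in PERSEPT 3, and that the first administration means the first dose here. The documents permit the first without describing it. They support the second through enrolment and AE collection at consent, and the third through the wording of the SAP.

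The effect falls mainly on milder or unrecognised reactions in patients coming from PERSEPT 2. Their number is not given, the PERSEPT 2 protocol is not available, and 21 days is a calendar maximum rather than time on drug. The 8.3 to 16.7 point illustration depends on an assumed 6 to 12 patients. The documents do not support a claim that safety events are hidden or that the trial's safety conclusion would change.

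**What to change.** 1. In Protocol 6.9.2, state that until the first PERSEPT 3 dose, AEs of a patient still enrolled in PERSEPT 2 are collected as AEs in PERSEPT 2, and may also be listed here as pre-treatment. From the first PERSEPT 3 dose, they are collected in PERSEPT 3.
2. In Protocol 6.9.9, 9.6 and SAP 7.8.2, define the first LR769 administration as the first dose for the PERSEPT 3 procedure.
3. If collection is to stay in PERSEPT 3 only, show AEs with onset after consent and following a PERSEPT 2 dose of LR769 in a separate row, not pooled with perioperative TEAEs.

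The cost is wording in these sections and, under item 3, one derived flag. The dosing data for that flag should already be available here, because Protocol 5.5 records concomitant therapies with date, time and dose from 30 days before screening. The sponsor should check that the PERSEPT 2 protocol carries a matching rule.
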